### **Sample Size and Power Considerations**

Frequentist Analyses With regard to sample size, the current proposal is limited to a maximum credible sample of  $N = 20$  ( $n = 10/\text{group}$ ) that may be accrued in the given time window and the budget of the funding mechanism. While the specific analyses proposed above will be thoroughly evaluated, ultimately the research proposed here will be exploratory and hypothesis-generating for the purpose of a larger-scale trial. Given these limitations, frequentist power calculations are presented as due diligence for the current proposal (conducted via G\*Power 3.1.9.4) and focus on the broadest analytic goal presented by Hypothesis 1 (change over time for each treatment group for a given relapse risk outcome). Assuming alpha = 0.05, a maximum credible sample size  $N = 20$  (10/group) provides 80% power to detect a large effect size Cohen's  $f = 0.66$ .

Bayesian Analyses An advantage of the dual frequentist/Bayesian approach is that current proposals are able to utilize the ability of Bayesian inference to provide probabilistic estimates of effects even in the context of small sample sizes.

of lower power to detect small effect sizes. Given the exploratory nature of the present research, Bayesian analyses will focus on posterior probabilities  $\geq 0.75$  (equivalent to a Bayes factor = 0.33 or 3.0) to emphasize the value in discerning a signal for model effects across analyses.

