## DATA ANALYSIS PLAN

**Confounding Variables** Preliminary data analyses will inspect relationships between baseline/demographic variables, experimental group, and specified outcome variables via traditional statistical tests (e.g., chi-square, Mann-Whitney-Wilcoxon, Kruskal-Wallis, and *t*-tests). Baseline covariates that demonstrate a relationship with both assigned group and outcome variables meet criteria for being potential confounders and will be included as a covariate in any statistical models for hypothesis testing. All analyses will statistically control for the stratification variables (detailed above in the Study Design section).

**Inferential Paradigm** Following recommendations for clinical trials in the literature analyses will proceed using parallel frequentist and Bayesian statistical inference. Frequentist results yield The probability of the data (or data more extreme), given the null hypothesis, while Bayesian results yield The probability of the null hypothesis given the data and The probability of the alternative hypothesis given the data.

alternative hypothesis. If possible, Bayesian analyses will incorporate informative priors as they develop in the literature; otherwise, weakly informative priors will be incorporated as a default (e.g., for regression coefficients:  $\sim N[\mu=0, \sigma^2=100]$ ; for non-linear outcomes this prior applies to the coefficient within the link-function). Sensitivity analyses using optimistic and pessimistic, skeptical priors will evaluate prior assumptions. Assessing the convergence of Bayesian analyses on the posterior distributions via Monte-Carlo Markov chain (MCMC) will use graphical (Trace Plot, Autocorrelation Plot) and quantitative (Geweke Diagnostics, Gelman-Rubin Diagnostics, and Heidelberger-Welsh Diagnostics) evidence. Evaluation of posterior distributions will permit statements regarding the probability that effects of varying magnitudes exist, given the data. Statistical analyses will use SAS v. 9.4 and the most up-to-date stable release version of the R statistical computing environment using packages rstan and brms.

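### The stated match between a posterior probability of 0.75 and a Bayes factor of 3 holds only at prior odds of 1, which the plan does not require of its preferred informative priors

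*Combined protocol and SAP*

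**What the plan says.** In Sample Size and Power Considerations, the plan states that "Bayesian analyses will focus on posterior probabilities" of at least 0.75, and describes that level as "equivalent to a Bayes factor = 0.33 or 3.0". It names no prior and no prior odds there, and gives no other Bayesian threshold.

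The priors are set out in the Data Analysis Plan, under Inferential Paradigm. The first choice is informative: "If possible, Bayesian analyses will incorporate informative priors as they develop in the literature". Otherwise a weakly informative default is used; the example given for regression coefficients is normal with mean 0 and variance 100. In addition, "Sensitivity analyses using optimistic and pessimistic, skeptical priors will evaluate prior assumptions". No mean or SD is given for the informative, optimistic, pessimistic or skeptical priors, and no date by which they must be chosen.

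The same paragraph describes the target of inference in more than one way. It refers to "The probability of the null hypothesis given the data" and also to "statements regarding the probability that effects of varying magnitudes exist, given the data". The hypotheses in Primary Hypotheses and Specific Aims are directional.

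**The concern.** A Bayes factor measures how far the data shift the odds. A posterior probability combines that shift with the odds held beforehand. The two can stand for one threshold only if the starting odds are fixed at 1, and the plan does not say this.

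This matters because the default prior, for which the statement is right, is the fallback. The preferred informative prior may already lean towards benefit. With 10 participants per arm such a prior can carry much of the weight, and a result labelled as a signal at a Bayes factor of 3 could rest on data that lowered the probability of benefit. Because priors are to be taken up as they appear in the literature, with no cut-off date, the wording also leaves room for a prior to be chosen after data have been seen. The results are meant to support a later grant application (Abstract, Proposed Study), so a reader needs to know which part of a signal came from this trial.

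**Working it through.** **Inputs from the documents.** Threshold 0.75 and Bayes factor 3.0 or 0.33; 10 per group (Sample Size and Power Considerations). Default prior N(0, variance 100), so SD 10 (Inferential Paradigm).

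**Assumed, because the plan gives no figures.** The locations and spreads of the shifted priors below. The effect is expressed in SD units with SD 1, so SE = √(1/10 + 1/10) = 0.447 and the data variance is 0.2.

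**1. The plan's own figure.** Posterior odds = Bayes factor × prior odds. At prior odds of 1, 0.75/0.25 = 3.0 and 0.25/0.75 = 0.33. The figure reproduces exactly. Under N(0, 100), P(effect > 0) = 0.5, so the prior odds are 1 and the statement is correct for a directional hypothesis. It is also correct when null and alternative are each given prior probability 0.5.

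**2. Other prior odds.** For prior probability p, the Bayes factor needed to reach 0.75 is 3 × (1 − p)/p.

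| Prior probability of the hypothesis | Bayes factor needed |
|---|---|
| 0.25 | 9.0 |
| 0.40 | 4.5 |
| 0.50 | 3.0 |
| 0.60 | 2.0 |
| 0.75 | 1.0 |
| 0.90 | 0.33 |

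**3. When the prior alone is enough.** For a N(m, s²) prior, P(benefit) = Φ(m/s). This reaches 0.75 at m/s = 0.674. Any normal prior centred at least that far towards benefit meets the threshold with no data.

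**4. Illustrations with 10 per arm.** Posterior variance v = 1/(1/s² + 1/0.2), and posterior mean = v × (m/s² + d/0.2). The rule is met when the posterior mean is at least 0.674 × √v.

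For N(0.5, 0.4²): v = 1/(6.25 + 5) = 0.0889 and √v = 0.298, so the mean must reach 0.201. The mean is 0.0889 × (3.125 + 5d) = 0.278 + 0.444d, so d = (0.201 − 0.278)/0.444 = −0.17.

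| Prior | Prior P(benefit) | Bayes factor needed | Smallest observed d that meets 0.75 |
|---|---|---|---|
| N(0.5, 0.5²) | 0.84 | 0.57 | 0.005 |
| N(0.5, 0.4²) | 0.89 | 0.35 | −0.17 |
| N(0.5, 0.3²) | 0.95 | 0.15 | −0.57 |
| N(−0.5, 0.5²) | 0.16 | 15.9 | not computed |

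A Bayes factor below 1 means that the data lowered the probability of benefit under that prior. In the first three rows the threshold can be met in that situation.

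**5. The event must be named too.** Under the default prior, P(effect > 2) is 0.421 in coefficient units, so 0.75 needs a Bayes factor of 3 × 0.579/0.421 = 4.13. For P(effect > 5), with prior probability 0.309, it needs 6.72. Even with the default prior, the equivalence to 3 applies to direction and not to effects beyond a chosen size.

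**The case against.** The best defence is that the figure is right where it is most likely to be used. The hypotheses are directional, the default prior is centred at zero, and informative priors apply only if they are available. Optimistic priors are confined to sensitivity analyses and paired with pessimistic, skeptical ones; leaning towards benefit is their purpose. The trial is declared exploratory, no decision or efficacy claim hangs on 0.75, and frequentist results are reported alongside. All of this stands and lowers the severity. It does not supply the missing condition, and informative priors remain the first choice.

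A reader might infer more than the documents support:

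- *That the figure is wrong for most of the planned analyses.* This cannot be shown. No prior locations are given, an informative prior may have odds of 1, and a skeptical prior centred at zero does have them. Nor does the plan expressly apply 0.75 to the sensitivity priors.
- *That any optimistic or informative prior passes on null data.* It depends on the prior. With N(0.5, 0.5²) and an observed effect of zero, the posterior is 0.7475, just short. The negative thresholds above come from tighter priors that are illustrative.
- *That a directional posterior and a point-null Bayes factor will contradict each other under the default prior.* The plan specifies no point-null analysis, and the result depends on outcome scale. At d = 1 the point-null Bayes factor is 0.54 if the outcome SD is 1, but about 3.3 if it is 10.
- *That the sponsor intends to choose priors after seeing results.* Nothing says so. The wording only fails to rule it out.

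**Conclusion.** The concern holds in a limited form. Equating 0.75 with a Bayes factor of 3 is correct at prior odds of 1 and not otherwise, and the plan states the equivalence without that condition while preferring priors that need not satisfy it. The Bayes factor actually required runs from 9.0 at a prior probability of 0.25 to 0.33 at 0.90, and a normal prior with m/s of 0.674 or more towards benefit needs no data at all.

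Those results are exact. The observed-effect thresholds rest on assumed priors and on a standardised SE of 0.447, and show what the rule permits, not what will happen. Severity is low to moderate: the trial is exploratory, but the omission affects how a signal from 20 participants would be read.

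**What to change.** 1. State that the 0.75 rule refers to the directional posterior probability, and that it equals a Bayes factor of 3 only at prior odds of 1, as under the zero-centred default prior.
2. Always report the result under that default prior. Under any informative, optimistic or pessimistic prior, report the prior probability and the Bayes factor (posterior odds divided by prior odds) beside the posterior. Do not call a signal from the trial when 0.75 is reached with a Bayes factor of 1 or less.
3. Fix every prior, with its location and spread, in writing before unblinding, and remove the allowance for priors to be taken up as the literature develops.

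Judging the Bayes factor alone against 3 would be a poor substitute. Under N(−0.5, 0.5²) the prior odds are 0.159/0.841 = 0.189; a Bayes factor of 3 gives posterior odds of 0.566, a probability of benefit of only 0.36. Both quantities should be shown.

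The cost is SAP wording, the choice of priors made in advance, and one extra ratio per model. No additional data are needed.

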## DATA SAFETY MONITORING PLAN

### **E1. Human Subjects Involvement and Participant Characteristics**

The study will test 20 current cigarette smokers, 18 to 65 years old that report smoking at least 10 cigarettes/day (half pack). Notably, because the study medication (suvorexant) is contraindicated with alcohol use, we will exclude subjects with alcohol use disorders (via screening at intake). We will also exclude those individuals meet DSM-5 criteria for an alcohol use disorder or report recent problem drinking (5/4 drinks for males/females in < 2.5 hours or > 10 alcoholic drinks per week) or those who report being unwilling to stop using alcohol in the evening for the two weeks of the study. Additional exclusion criteria include individuals that are pregnant, nursing, or planning on becoming pregnant during the course of the study; or if they have any other illness, condition, or use of medications which in the opinion of the PI and/or admitting physician would preclude safe and/or successful completion of the study. This will be accomplished via full medical evaluation at intake by [name], M.D., CNRA Medical Director. The study will be conducted at the Neurobehavioral Research Laboratory at the CNRA. Recruitment strategies will include local advertising in print media, public service announcements on radio, and referrals to CNRA in the Houston metropolitan area. We expect to enroll a minimum of 2 participants per month to meet recruitment goals; however, we will be able to accommodate four simultaneous participants. Participants will be required to participate for 3 days (intake/screening, baseline observations, and one follow-up observation one week later). Research data will be collected at each scheduled time point.

**Exclusion criteria** will include: (1) meeting criteria for diagnosis with a substance use disorder on drugs other than nicotine or cannabis; (2) greater than moderate cannabis use; (3) have a DSM-IV axis I psychiatric disorder or neurological disease or disorder requiring ongoing treatment and/or making study participation unsafe; (4) significant current suicidal or homicidal ideation; (5) medical conditions contraindicating administration of suvorexant (e.g., severe pulmonary disease, severe cardiovascular disease or clinically abnormal EEG, severe liver or kidney disease, seizure disorder, or sleep disorder – particularly narcolepsy); (6) taking medications known to have significant drug interactions with the study medication(s) (e.g., MAO inhibitors, anticonvulsants, haloperidol, phenothiazines, anesthetics, and all sedatives); (7) currently or recently (last 3 months) treated for substance use [other than nicotine] or another psychiatric condition; (8) conditions of probation or parole requiring reports of drug use to officers of the court; (9) impending incarceration; (10) pregnant or nursing for female patients; (11) inability to read, write, or speak English [required for lab tasks and psychometric scales]; (12) unwillingness to sign a written informed consent form; (13) subjects with alcohol use disorders or report recent problem drinking (5/4 drinks for males/females in < 2.5 hours or > 10 alcoholic drinks per week). All subjects who are excluded will be given referral information to local treatment programs.

## **E2. Sources of Materials**

We will obtain information about subjects from structured interview evaluations, physical examinations, self-report measures, and computerized behavioral tasks. This information will be collected at specified time points during the study phases of intake, baseline assessment, experimental testing, and end-of-study. The biological specimens obtained from all subjects will include urine and breath samples for alcohol detection. Individuals who volunteer to participate will be assigned a subject number (e.g., 10500), under which all information collected will be filed. All materials will be obtained for the specific purposes of this research.

## **E3. Potential Risks**

**Suvorexant** (BELSOMRA) is an orexin receptor antagonist indicated for the treatment of insomnia, characterized by difficulties with sleep onset and sleep maintenance. Recommended dose is 10 mg, 1x per night taken within 30 minutes of going to bed, with at least 7 hours of planned time before awakening. If the 10 mg dose is well tolerated but not optimally effective, it can be increased but not to exceed 20 mg once daily. Medication is taken PO, with dosage in tablets of 5, 10, 15, and 20 mg. Contraindicated in patients with narcolepsy. Precautions include daytime somnolence; dose-related risk of impaired alertness and motor coordination, including impaired driving; patients taking 20 mg should be cautioned against next-day driving; nighttime “sleep-driving” and other complex behaviors while out of bed and/or not fully awake; worsening of depression or suicidal thinking; compromised respiratory function; sleep paralysis, hypnagogic/hypnopompic hallucinations. Risk of the above symptoms increases with use of CNS depressants and alcohol. In obese women (BMI > 30), there is increased risk of exposure-related adverse effects. Belsomra is a schedule-IV compound with mild/modest abuse-potential in the same class as existing sleep medications and anxiolytics. The most common adverse reactions include somnolence and slowed motor coordination. Not recommended for use in patients taking strong CYP3A inhibitors, efficacy may be reduced, or for patients with severe hepatic impairment. Based on animal data, Belsomra may cause fetal harm.

**Risks for Behavioral and Psychometric Testing.** Items on certain psychological/psychiatric questionnaires and interviews might be perceived as personally discomforting to some subjects. Similarly, subjects may experience discomfort due to withdrawal symptoms as part of the smoking relapse assessment. With regard to the actigraphy sleep monitoring, participants may experience mild discomfort while acclimating to wearing the device during sleep. While subjects may be uncomfortable reporting these issues, the risks of serious sequelae are extremely low.

**Risks for Cold Pressor Test.** Individuals with cardiovascular disorders and neurological disorders should not participate. This information will be obtained during medical screening. Due to individual variation in pain and cold sensitivity, for some subjects the cold water may become too painful to sustain immersion for 120 seconds. There are no lasting effects from placing the hand and wrist in ice water (0° Celsius) for 120 seconds.

**Risks for Physical Examination.** The intake screening and physical exam are part of the CNRA General Evaluation protocol, and are approved under protocol HSC-MS-05-0322 and detailed therein.

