**Research Team PI: [name].** [name] is an Assistant Professor in the Department of Psychiatry & Behavioral Sciences, with a primary research program involving novel applications of biostatistics and data science to health outcomes. However, his recent endeavors have expanded to first-hand research in substance use disorders and psychopharmacology, resulting in two pertinent first-author publications investigating (1) the effects of suvorexant on relapse-related factors in cocaine use disorder and (2) the strongest predictors of the first smoking lapse during a quit attempt. The present study will be supported by the infrastructure and research team at the CNRA, including **[name].**, a frequent collaborator of the PI that will assist in the implementation of the current experimental design, and mentorship from **[name].**, with expertise in psychopharmacology and the neurological bases for addiction.

**Study Medication & Medication Compliance** Participants will be randomized to receive either suvorexant 0 or 20 mg for 7 days. 20 mg is currently the highest FDA-approved dose. The bioavailability of suvorexant is > 80% and it is highly protein-bound, with a half-life of approximately 12 hours and plasma steady-state is reached within three days. Because suvorexant is a hypnotic with a moderate half-life, participants will be informed to take the medication at 10:00 PM. Compliance will be assessed using both Medication Event Monitoring Systems (MEMS) pill bottles that record the time/frequency of bottle openings as well as riboflavin.

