### **Measures**

**Baseline Screening** As part of the CNRA general evaluation protocol (HSC-MS-05-0322), to determine eligibility, participants will receive a comprehensive medical and psychiatric evaluation including: a medical-history questionnaire, physical examination, laboratory chemistries (e.g., blood chemistry screen, complete blood count, urinalysis and urine pregnancy test), and ECG. Clinicians will conduct the **SCID**, the **ASI**, the **KMSK** assessment of lifetime substance use interview, and **TLFB**.

**Smoking-Related Measures** Nicotine dependence will be assessed using the **FTND**. Self-report will be used to collect self-reported number of cigarettes used in the past 7 days. Nicotine craving will be assessed using a brief, 10-item version of the **Questionnaire of Smoking Urges (QSU-brief)**. Nicotine withdrawal will be assessed using the 8-item **MNWQ**. **Breath CO** will be used to measure severity of smoking and overnight smoking abstinence.

**Sleep-Related Measures** Quality of sleep in the past week will be primarily assessed using the **PROMIS Sleep Disturbance Short Form**, a well validated and reliable subjective measure of sleep quality. Secondary measures will include the **Epworth Sleepiness Scale**, and **PSQI**. Sleep actigraphy (total hours, levels, and movement) will be measured via the Garmin Vivosmart® 3 device as validated by recent research.

**Stress and Anxiety Measures** Stress and anxiety will be assessed using standard, validated questionnaires using the **HAM-A**, **PSS**, and **DASS-21**. Additionally, a single-item **VAS** measure will be used to assess self-reported stress.

**Human Laboratory Measures** Experimental measures will be conducted on study days 1 and 8. Participants will be instructed to stop smoking by 10 pm the day before, in order to ensure they meet the breath CO criterion ( $CO \leq 4$  ppm) indicating overnight abstinence. In addition to measuring nicotine craving and withdrawal using the QSU and MNWQ, respectively, we will conduct two additional assessments.

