**Stress Reactivity** Stress reactivity will be assessed using a modified version of the CPT on study days 1 and 8. The CPT involves participants submerging their dominant arm in an ice-water bath for up to 2 min. The CPT is widely used to induce stress in human laboratory studies and activates major stress systems in the body. Stress activation can be significantly increased by incorporating a social evaluative component, which will be done by having a study member present wearing a white lab coat and holding a clipboard. Participants will also be videotaped and informed that their facial expressions will be assessed. Stress levels will be assessed using both subjective and physiological measures, including HR, BP, and salivary cortisol, consistent with previous studies from our group.

**Smoking Relapse Assessment** A dual-component smoking relapse assessment will be conducted in which participants will have the opportunity to self-administer their preferred brand of cigarettes. Participants will earn \$1 for every 5 min they do not smoke for the first 50 minutes (for a total of \$10). At 50 minutes or once participants indicate they want to smoke, they will be given \$7 to either purchase their preferred brand of cigarettes (\$1 per cigarette) or keep. The two dependent variables will be latency to smoke the first cigarette and total number of cigarettes smoked.

**Study Compensation** Participants will be provided \$40 for completing the baseline screening. They will receive \$50 for attending each study visit and a \$50 bonus for completing the study/returning study equipment. Additionally, participants will receive \$5 compensation per visit for parking and/or bus fare. As noted above, participants may earn up to \$34 across visits during the smoking relapse assessment (if achieving maximum latency and zero cigarette purchase), bringing total possible compensation to \$234/participant. Upon study completion, participants may be given the opportunity to earn an additional \$20 for referring new participants to the study that successfully enroll and also complete all study procedures.

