## **E4. Adequacy of Protection Against Risks**

### **Procedures to Minimize Drug-Related Risks**

We will screen very carefully for alcohol use and depressive symptoms. It will be made explicit that participants are not to drink alcohol in evening. We will use the Alcohol Use Disorders Identification Test (AUDIT) score and our mental health counselors SCID-screener to enroll only those with low risk for alcohol abuse. Subjects will report no current depressive symptomatology (Beck Depression Inventory, or BDI < 15), with no past depressive episodes or suicidal ideation. The Columbia Suicide Severity Rating Scale (CSSRS) will be administered at each visit (see additional details below), as per NIH/FDA  UTHealth Houston s. Indication of regular IRB NUMBER: HSC-MS-19-0966 IRB APPROVAL DATE: 10/12/2023

alcohol use by AUDIT score, intake self-report, or breath alcohol, or indication of increase in depressive symptomatology / suicidality as measured by the CSSRS will result in study stopping (see details below). Will exclude for any patients taking CYP3A inhibitors; patients with severe hepatic impairment; and women who are or become pregnant. Pregnancy and drug tests are administered on via urinalysis on lab testing days. Women of childbearing capacity must be taking one form of birth control. We will exclude for women with BMI > 30 to decrease risk of side effects.

In addition to the rigorous screening criteria for inclusion. At the end of each experimental day, cardiovascular measures will be taken and the subject will be evaluated for signs of impairment or side effects, first by a research assistant and then by the research nurse, medical director, or PI. The assessment battery includes subjective effects questionnaire, nystagmus, touching nose, balance, and walking a straight line). If cardiovascular measures are normal, within the range of pre-dose levels, and the subject is determined to be unimpaired, the subject will be released. If any signs of intoxication are detected, participants will be required to remain at the experimental site until such symptoms are no longer observed.

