**Other Protections Against Risk.** The following procedures will be taken to safeguard against adverse medication events: (1) careful initial intake evaluation to determine eligibility based on inclusion/exclusion criteria; (2) thorough physical evaluation prior to treatment, consisting of physical examination, standard laboratory tests, electrocardiogram, toxicology screen, pregnancy test, and vital signs; (3) repeated tests during treatment; (4) daily monitoring of pill taking using MEMS caps, returned pill counts, and self-report; (5) weekly review of adverse events and medication compliance; (6) regular evaluation by the study physician ([name]). Specific criteria will be used to exclude potential subjects for whom any of the study medications is contraindicated. Any abnormal physiological, psychological, or behavioral event will be evaluated and, if indicated, will result in the subject's removal from the study.

For all three experiments included in this project, we will use an Adverse Event Log (AEL) based on NIDA SAFTEE procedures. The AEL will record the duration, severity, and frequency of any adverse events, signs, and symptoms. An evaluation will be made as to the event's relationship to the study drug(s), scaled as unrelated, unlikely, possible, and probable. The AEL will be included in 1   IRB APPROVAL DATE: 10/12/2023

Subjects will be monitored regularly for compliance with the study requirements, including the dosing regimen and breath alcohol testing upon arrival at the laboratory each day of testing. Written and verbal information about the medication will be given to all participants. This information will remind the subject to: (1) take food shortly after medication if needed to relieve gastric irritation; (2) inform the treatment research clinic nurse or physician of any over-the-counter and prescription medication taken, especially: cough medication, diarrhea medication, narcotic medication; (2) notify treatment research clinic nurse or physician of any side effects that persist or worsen. The study physician, nurse, and PI will review cases involving clinical deterioration of increased symptomatology or substance abuse. Appropriate actions will be taken, including study termination with proper referral.

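### Day 8 latency is tested the day after the seventh dose with no sedation measure named before the tasks, so a longer wait cannot on its own be read as lower relapse risk

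*Combined protocol and SAP*

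**What the plan says.** **Dosing and testing.** Under Study Medication & Medication Compliance, "Participants will be randomized to receive either suvorexant 0 or 20 mg for 7 days", and "participants will be informed to take the medication at 10:00 PM". The drug is described there "with a half-life of approximately 12 hours and plasma steady-state is reached within three days". Table 1 shows the supply handed out on Day 1. Under Human Laboratory Measures, "Experimental measures will be conducted on study days 1 and 8".

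**Latency task.** Under Smoking Relapse Assessment, participants earn $1 for each 5 minutes without smoking, for up to 50 minutes. The wait ends early only if the participant asks to smoke. Hypothesis 1 predicts longer latency on suvorexant.

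**Sedation and driving.** E3 warns that "patients taking 20 mg should be cautioned against next-day driving" and names sleepiness and slowed coordination as the most frequent adverse reactions.

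**Impairment checks.** E4 (Procedures to Minimize Drug-Related Risks) states: "At the end of each experimental day, cardiovascular measures will be taken and the subject will be evaluated for signs of impairment". E10 (Safety of Research Participants Outside of the Research Site) repeats the battery for each visit without a time, but ties it to release. The only arrival check that E4 (Other Protections Against Risk) names is breath alcohol.

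**Information and travel.** The medication reminders in E4 begin with "1) take food shortly after medication if needed to relieve gastric irritation" and go on to other medicines and side effects; driving is not listed. Participants receive $5 "compensation per visit for parking and/or bus fare".

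**The concern.** Two separate issues arise from the same timing.

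The first is interpretation. Latency is offered as a marker of relapse risk, but the task rewards doing nothing. A drowsy participant who simply sits through the wait gets the maximum score and the full $10. Sedation therefore pushes latency the same way as the hypothesised benefit. The model under Specific Analyses has no sedation term and no supportive analysis to tell the two apart. The one objective impairment battery with a stated time comes after the cold pressor and relapse task. The pilot is meant to support a later grant application, so a misread latency signal would carry forward into the next trial's rationale.

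The second is consistency. E3 states a caution about the day after a 20 mg dose, Day 8 is such a day for every active participant, and none of the procedures in the supplied text carries that caution out.

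**Working it through.** No figure in the plan is in dispute. As a check on the design used below, the stated 80% power reproduces: with f = 0.66, N = 20 and degrees of freedom 1 and 18, the noncentrality is 0.66² × 20 = 8.71 and the noncentral F gives 79.7%.

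**1. Time since dose.** Seven nightly doses starting on Day 1 end on the evening of Day 7. E10 refers to daytime participation but gives no clock time. Assume Day 8 tasks between 8 AM and 2 PM, that is 10 to 16 hours after 10 PM, or 10/12 = 0.83 to 16/12 = 1.33 half-lives.

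**2. Drug remaining.** Assume first-order decline and ignore absorption. The fraction left is 2^(−h/12):
- h = 10: 2^(−0.833) = 0.561
- h = 16: 2^(−1.333) = 0.397

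So 56% to 40% of that dose's level remains. This shows drug on board; it does not measure impairment.

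**3. Effect on latency in minutes.** Suppose a share q of the active arm sits out the 50 minutes through drowsiness and would otherwise have waited m minutes on average. The arm mean rises by q × (50 − m). With q = 0.2 and m = 25 this is 5 minutes. Over q from 0.1 to 0.3 and m from 35 down to 15, it runs from 0.1 × 15 = 1.5 to 0.3 × 35 = 10.5 minutes. Both q and m are assumptions.

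**4. Effect on the plan's signal threshold.** Sample Size and Power Considerations uses a posterior probability of at least 0.75. Read this as the probability that the effect favours suvorexant, and take a near-flat prior and a simple comparison of 10 per group. The standard error in SD units is √(1/10 + 1/10) = 0.447. If sedation alone shifts latency by s SD, the chance of crossing the threshold is Φ(s/0.447 − 0.674). The last column uses the noncentral t with 18 degrees of freedom.

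| Assumed shift s (SD) | Chance of posterior ≥ 0.75 | Chance of two-sided p < 0.05 favouring suvorexant |
|---|---|---|
| 0 | 25% | 2.5% |
| 0.2 | 41% | 6% |
| 0.3 | 50% | 9% |
| 0.5 | 67% | 18% |

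The documents give no size for a sedation effect on latency, so s is illustrative.

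**5. Where sedation could be observed on Day 8.** The timed battery follows the tasks, the untimed one is linked to release, and arrival has breath alcohol only. Epworth is collected as a secondary sleep measure and does not capture momentary sedation. On Day 1 the battery precedes any drug, so it can serve as a reference, but only for the same point in the visit.

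**The case against.** **The randomised contrast is sound.** A reader might infer that sedation biases the latency comparison. It does not: sedation is an effect of the drug, and the contrast is valid as a total effect. Having drug on board is also consistent with testing orexin antagonism. This stands. Only the reading of the contrast as reduced relapse drive is in doubt.

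**The study is exploratory and latency is not alone.** Craving, withdrawal and number of cigarettes are also collected, Epworth gives some sleepiness data, and exploratory analyses are left open. This lowers the stakes, but none of these shows how sedated a participant was when the wait began.

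**The driving caution may be met.** A reader might infer that the protocol breaches its own caution. The documents do not support that. The consent form was not available for this review. E4 promises written and verbal medication information and a consent form that describes the risks, and E10 promises full disclosure of side effects. The reminder list is not stated to be exhaustive.

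**Paying for parking does not show that driving is expected.** The $5 covers bus fare equally, and E4 mentions public transit for the trip home.

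**The late check is not the only safeguard.** E10 gives no time for its battery. Keeping an impaired participant on site and arranging a taxi apply whenever someone does not seem well. Those provisions cover the trip home; the state during the tasks and the trip in remain unaddressed in the supplied text. The E4 reference to pre-dose levels may simply mean Day 1.

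**A coarse battery in 10 per arm will yield few events.** True, so it can support only descriptive reporting.

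**Conclusion.** The point holds as a limit on interpretation that is cheap to reduce. The documents themselves establish that Day 8 follows the seventh dose, that the half-life is about 12 hours, that passivity scores as maximum latency, and that no momentary sedation measure is named before the tasks. The 56% to 40% range rests on assumed clock times and first-order decline. The rise from 25% to about 50% in the chance of a Bayesian signal rests on an assumed 0.3 SD shift and a near-flat prior. The plan's default prior has variance 100 on the coefficient and could pull these chances down if latency is modelled in minutes.

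The driving caution is a separate matter of reconciliation: the supplied text shows no procedure that carries it out, and nothing stronger can be said without the consent form.

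**What to change.** 1. Give the existing impairment battery before the cold pressor and relapse task on Days 1 and 8, as well as at release.
2. Derive hours since the last dose from the MEMS data already collected.
3. Report both by arm beside latency as supportive information. Neither should replace or adjust the main estimate: sedation arises after randomisation and is part of the drug's effect.
4. State in advance that a latency difference accompanied by pre-task impairment will not on its own be read as reduced relapse risk.
5. Separately, the sponsor should reconcile the driving caution in E3, the travel payment (Study Compensation, E5 and E10), the reminders in E4, and the timing of the impairment check in E4 and E10. No driving, travel or dosing rule is proposed here.

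The cost is about 10 minutes more per laboratory visit, with existing staff and tools, and more guarded claims from latency.
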